## Self-harm and suicidality measures

A brief bespoke measure of self-harm and suicidality will be used to collect information directly from the young people in the trial at baseline, 12 weeks, 6 months and 12 month

follow up post randomisation. The measure has been designed with expert input from depression specialists. Questions will ask about suicide attempts, self-harm and thoughts about suicide. This will be asked firstly in relation to the past 6 months at baseline. The subsequent follow-ups will ask about self-harm and suicide attempts since the previous timepoint.

# Behavioural Activation for Depression (BADS)

The BADS-SF is a 9-item questionnaire, based on the longer, 25-item BADS (Kanter et al., 2007; Manos, Kanter and Luo, 2011) that measures levels of activity on 2 sub-scales: activation (goal-directed action and completion of scheduled activities) and avoidance (procrastination rather than active problem solving). The BADS-SF consists of 9 questions, each rated based on the previous week on a seven-point scale ranging from 0 (not at all) to 6 (completely); higher scores represent increased behavioural activation. Total scores on the BADS-SF range from 0 to 54. We will use the BADS-SF to monitor self-reported activity and avoidance. Although the scale has not been validated with an adolescent population, we will use it as there are no alternative similar tools to help us explore behavioural activation as a mediator for changes in depression symptoms.

# Child Health Utility-9 Dimensions (CHU-9D)

We will use the CHU-9D (Stevens, 2010) to derive health utility and calculate quality-adjusted life years (QALYs). The questionnaire consists of 9 domains, each with 5 statements (scored 1–5) that will assess the young person's functioning across domains of worry, sadness, pain, tiredness, annoyance, school, sleep, daily routine and activities on that specific day. For example: 1= I don't feel sad today, 2=I feel a little bit sad today, 3=I feel a bit sad today, 4=I feel quite sad today, 5=I feel very sad today. The responses under the 9 domains can be taken together as a description of the young person's "health state" using a descriptive system that combines all responses across all items (e.g. 11232152). Different utility weights were assigned to each level of each domain. Different combinations of responses across the 9 dimensions therefore result in different health states that have a utility value on a 0–1 scale, where 1 is perfect health and 0 is equivalent to being dead. The UK young people valuation set will be used to derive the utility values (Stevens, 2012). Utility values from each time point in the trial will be used to calculate quality-adjusted life years (QALYs) which will be the measure of health benefit in the economic evaluation.

### EQ-5D-Y

This will be completed by participants. The EQ-5D-Y comprises five dimensions of health: mobility, looking after myself, doing usual activities, having pain or discomfort and feeling worried, sad or unhappy. Each dimension has 3 levels: no problems, some problems and a lot of problems (EURO-QOL Research Group, 2018). As with the CHU-9D, each profile of responses can be converted into a utility value. We will use the valuation method recommended by the National Institute of Health and Care Excellence (NICE) at the time the analysis is conducted.

# **EQ-5D-5L**

This will be completed by carers, in relation to their own health. The EQ-5D-5L consists of 5 dimensions of health: mobility, self-care, usual activities, pain, anxiety/depression. Each dimension has 5 levels: no problems, slight problems, moderate problems, severe problems and extreme problems (EURO-QOL Research Group, 2018). Each profile of responses will be converted into its respective utility value according to the method recommended by NICE at the time the analysis is conducted.

# Adapted Child and Adolescent Service Use Schedule

We have adapted the Child and Adolescent Service Use Schedule (CA-SUS) for completion by participants, with assistance from their parent/carer. Its purpose is to collect information about use of health and social care by each young person during the study period. This will be used to estimate costs for the economic evaluation. To incorporate a broader perspective, the schedule also captures information on the amount of time parents/carers spend with YP at health and social care contacts. The questionnaire has been reviewed by PPI panel members and revised based on their feedback.

## Goal Based Outcome measure

Young people will be asked to work with the Research Assistant to set a goal for themselves to work towards, which will be measured on a Likert scale of 0 to 10, 0 goal met 'none of the time' and 10 being goal met 'all of the time' (Law, 2013). This will evaluate clinical progress throughout either behavioural activation or treatment as usual. YP will set a primary goal for the purpose of the trial (related to their mental health) during the baseline appointment with the RA and will be asked to review the goal using the Likert scale at each follow-up. The measure allows the YP to personalise their care.

#### Aspects of Care Questionnaire

We developed the Aspects of Care Questionnaire (based on the COMBAT study measure) that has 4 items to help assess contamination, i.e. where an individual randomised to treatment as usual has inadvertently or intentionally received elements of BA. The items are 4 statements that correspond to BA-specific activities: 1. "I talked to my therapist about the things and people that I value in my life." 2. "I made plans for activities I enjoy and necessary tasks/routines in a weekly activity diary." 3. I wrote down things I did for pleasure and necessary tasks/routines in a weekly activity diary." 4. "I gave an ACE score (Achievement, Closeness, Enjoyment) to activities I completed in a weekly activity diary." Responses to each item are: 'yes, 'no' or 'I don't know'. Participants in the intervention group would be expected to answer 'yes' whereas participants randomised to treatment as usual would be expected to answer "no" or 'I don't know'.

#### Working Alliance Inventory (WAI-S)

The WAI-S aims to capture how the YP feels about their relationship with their BA therapist and to ensure there is a collaborative consensus between them. It measures 3 domains: a) agreement on the goals of the treatment; b) agreement about the tasks to achieve these goals; c) quality of the bond between therapist and YP (Hatcher and

Gillaspy, 2006). YP will be asked to rate a series of statements on a 5-point Likert scale, ranging from 1 (rarely or never) to 5 (always). The Goal, Task and Bond domains each have scores ranging from 5-20 and higher scores indicate better therapeutic alliance. (Paap & Dijkstra, 2017).

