#### 3.3. Quantitative Outcomes

Measures will be administered to participants by a trained researcher at baseline (n=446), 12 weeks (n=446), 6 months (primary outcome, n=446), and 12 months post-randomisation (naturalistic follow up, n= approx. 300/participants recruited  $\geq 12$  months before trial end date). All measures and their time-points of completion are presented in Table 1.

 Table 1: Summary of assessments

			TIMELINE				
Assessment	Source	Method of Completion	Screening	Baseline	12 Weeks	6 Months	12 Months *
			PARTICIPANT- YOU	NG PERSON			
Screening	Screening Log	Research Assistant (RA) /Site staff	X				
Mood and Feelings Questionnaire (MFQ-C)	Questionnaire	Self-completion	X	Х	Х	Х	X
Contact Details	CRF	Research Assistant/Participant		X	YTU to be notified of changes to contact details		itact details
Demographics	CRF	Self-completion/RA assistance if requested		X			
Eligibility (including Inclusion and Exclusion Criteria)	CRF	PI/Research Assistant/PIs Delegate at site		Х			
Consent	Paper/Online Consent Form/REDCap	Self-completion / Research Assistant		Х			
Strengths & Difficulties Questionnaire (SDQ)	Questionnaire	Self-completion/RA assistance if requested		X	Х	Х	X
Development and Well- Being Assessment (DAWBA)	Online	RA led alongside participant if requested		X			
Revised Children's Anxiety and Depression Scale (RCADS) Brief Version	Questionnaire	Self-completion/RA assistance if requested		Х	Х	Х	Х

Behavioural Activation for Depression (BADS)	Questionnaire	Self-completion/RA assistance if requested		X	Х	X	X				
Self- harm & suicidality questions	CRF	Self-completion/RA assistance if requested		Х	Х	Х	Х				
Goal based outcomes	CRF	Self-completion/RA assistance if requested		X	X	Х	X				
Child Health Utility -9 Dimensions (CHU-9)	Questionnaire	Self-completion/ RA assistance if requested		Х	Х	Х	X				
EQ-5D-Y	Questionnaire	Self-completion/RA assistance if requested		X		Х					
Healthcare Service Use schedule	CRF	Self-completion (with assistance from carer)		X	X	Х	X				
Aspects of Care Contamination Checklist	CRF	Self-completion/RA assistance if requested			X	Х	X				
Working Alliance Inventory (WAI-S)	Questionnaire	Self-completion	(Collected halfway through intervention delivery)								
End of BA treatment Questionnaire	Questionnaire	Self-completion	(Collected after final session of BA therapy)								
Optional Qualitative Interview	Semi-structured interview	Interview				X					
			PARENT/CA	RER							

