Consent	Paper/Online Consent Form/REDCap	Self-completion / Research Assistant		X							
Demographics	CRF	Self-completion/ RA assistance if requested		X							

Strengths & Difficulties	Questionnaire	Self-completion/RA								
Questionnaire (SDQ)-		assistance if requested		X	X	X	X			
Parent version		·								
Development and Well- Being Assessment	Online	RA led alongside		X						
(DAWBA)		participant if requested								
Mood and Feelings		Self-completion/RA								
Questionnaire (MFQ)  Parent version	Questionnaire	assistance if requested		Х	X	X	X			
Carer EQ-5D-5L	Questionnaire	Self-completion/RA assistance if requested		Х		X				
Generalised Anxiety Disorder (GAD-7)	Questionnaire	Self-completion/RA assistance if requested		х		Х				
Patient Health Questionnaire (PHQ-9)	Questionnaire	Self-completion/ RA assistance if requested		х		X				
Optional Qualitative Interview	Semi-structured interview	Interview				Х				
		R	ESEARCH ASSISTANT/I	RESEARCH TEAM						
						(X – IF				
Treatment as Usual	Questionnaire	Self-completion/Clinical				PARTICIPANT IS				
Questionnaire		records				NOT DUE A 12	X			
Questionnane		records				MONTH FOLLOW-				
						UP)				
Safety Reporting	CRF	Research								
		Assistant/PI/Clinician								
BA Completion (Discharge Information)	CRF	Clinician/Research Team			X (collected throughout)					
Trial withdrawals	CRF	Research Assistant/PI/Clinician	X (collected throughout)							

Table 2: Summary of BAY therapist assessments.

Assessment	Source	Method of Completion										
			Pre- trial	1 st session	2 nd session	3 rd Session	4 th Session	5 th Session	6 th Session	7 th Session	8 th Session	End of trial
			delivery	Session	30331011	Session	Session	30331011	30331011	30331011	30331011	triai
BAY THERAPIST												
Demographics	CRF	Therapist	Х									
BA Session Log	Questionnaire	Therapist		X	X	X	X	X	X	X	X	
Safety Reporting	CRF	Therapist	X (collected throughout)									
End of BA treatment Questionnaire	Questionnaire	Therapist									X (after final session)	
Fidelity to BA Checklist*	CRF	Independent Assessor										Х
Qualitative Interview	Semi- structured interview	RA led										х

\* Random selection of recordings based on pre-selection criteria: commence in year 2 of trial

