# End of treatment questionnaire

# - Young People

After their final session, YP will complete end of treatment questionnaires which will measure engagement with the intervention via self-report, website acceptability, preference for mode of delivery and any barriers to treatment. These will be distributed by an unblinded member of the research team. Young people who withdraw from the intervention before their 8th session will be asked to complete this measure at the point they stop their BA sessions. The questionnaire will generate quantitative and qualitative data which will contribute to overall acceptability measures.

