#### - Therapists

BA therapists will complete bespoke questionnaires when they have completed delivering all therapy sessions. End of treatment questionnaires will address acceptability of the intervention, acceptability of using a digital platform, preferences for mode of delivery, and any barriers faced during treatment. End of treatment questionnaires will be distributed by an unblinded member of the research team and will generate a combination of quantitative and qualitative data, which will contribute to overall acceptability measures of the intervention.

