#### 7.3. Procedure

Following informed consent/assent the young person will be assigned a participant number and will be asked to complete a series of standardised measures with a trained researcher captured on paper or electronically using REDCap (Research Electronic Data Capture).

The young person will conduct the MFQ at baseline with the researcher. Those with a score ≥27 MFQ will go on to complete the full baseline assessment. Those who do not meet the threshold will not be recruited on to the study and will continue to receive treatment as usual (this will be explained to the participant prior to giving consent).

The full baseline assessment will include: demographic questionnaire, DAWBA, SDQ, RCADS, WAI-S, CHUD-9D, EQ-5D-Y, WHO scale, suicidality questions, service use, GBO.

The carer will complete: MFQ, DAWBA, SDQ, and EQ-5D-5L on behalf of their child's mental health and PHQ and GAD-7 to report their own mental health.

On completion of the baseline measures, participants will be randomised to either receive BA+PE+treatment as usual or treatment as usual +PE.

A member of the trial management research team will inform the participant (and their carer, if applicable) and the BAY therapist if randomised to receive BA (and their clinical supervisor) and inform the participants GP via letter of the randomisation outcome. Upon informing the participant of their allocation, the trial managers will distribute the psychoeducation leaflet to the participants.

If randomised to BA, treatment sessions will be arranged by the local BA therapist who will liaise with the young person and, if appropriate, their carer (e.g for children aged between 11-15 years). Trial Managers will distribute a session log for the BA therapist to complete online/ on paper upon completion of each BA session delivered. Session logs will collect information about whether the session was recorded, whether the session was in-person or remote, who was present in the room and any problems encountered during the session.

If randomised to TAU+PE alone, the local manager will arrange treatment as usual as required. The researcher will arrange follow-up meetings at 12 weeks, 6 months and 12 months from the point of randomisation and will keep in contact with the young person before these meetings as needed. Participants will only be asked to complete the 12 month follow-up if they are recruited before July 2024 due to the study completion date (August 25).

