# 10.2. Participants and sample size

# Young people and Carers

During the internal pilot, we will seek to identify and recruit 15 'early exit' participants who initially consent but who do not commence the BAY intervention. These young people and/or their designated carer (where available) will be invited to participate in a qualitative interview to explore potential barriers and enablers to intervention commencement.

Across the internal pilot and main trial phases, we will complete one-to-one qualitative interviews with 25-30 young people and 25-30 carers per arm (~120 interviews) to explore intervention acceptability. Participants recruited in the internal pilot phase (max n=10-12) will additionally be asked about their experiences of trial recruitment and research processes.

Eligible participants will be the cohort of participants who consented at trial recruitment/baseline to be contacted about an interview, as recorded on the YTU database. We will purposefully sample across sites, and intervention engagement levels (<4, 4+ sessions), and use maximum variation sampling to ensure a spread of participants in terms of age, gender, SES and baseline depression severity.

The final sample sizes for the young people and carer samples will be determined by data saturation; we will continue to recruit until team consensus suggests saturation has been achieved. Participants may include but not depend upon, recruiting young people-carer dyads.

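### The WAI-S has one mid-treatment time point and no rule for young people who stop BA before it, so alliance is scored only in those who stay; its baseline listing and its stated score range are also wrong

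*Protocol*

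**What the plan says.** Section 3.3.1 gives the purpose of the WAI-S: "The WAI-S aims to capture how the YP feels about their relationship with their BA therapist". Table 1 in section 3.3 gives its timing as a single entry: "Collected halfway through intervention delivery". Neither place says what happens if BA ends before that point. Section 7.3 places it elsewhere: "The full baseline assessment will include: demographic questionnaire, DAWBA, SDQ, RCADS, WAI-S". That battery is completed before randomisation.

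On scoring, section 3.3.1 has items rated from 1 to 5 and then states: "The Goal, Task and Bond domains each have scores ranging from 5-20 and higher scores indicate better therapeutic alliance".

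Two neighbouring forms are handled differently from each other. For the young person's end-of-treatment questionnaire, section 3.3.1 says that those who leave before session 8 "will be asked to complete this measure at the point they stop their BA sessions". For the therapist's version it says: "BA therapists will complete bespoke questionnaires when they have completed delivering all therapy sessions". Table 2 enters the therapist form in the session 8 column as "X (after final session)".

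Section 10.2 samples interviewees across "intervention engagement levels (<4, 4+ sessions)", so the protocol already treats fewer than four sessions as a distinct group.

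**The concern.** A young person who attends one, two or three sessions and then leaves has met a therapist and could rate the relationship, but the schedule never asks. If a poor relationship is one reason for leaving, the missing scores are missing because of what they would have shown. The reported alliance would then be that of young people who stayed. The analysis cannot repair this, because the scores are never collected.

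The protocol recognises the problem for one form, the young person's end-of-treatment questionnaire, and solves it by collecting at the point of stopping. The WAI-S has no such rule. The therapist form has no clear one.

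The baseline listing and the score range are separate errors in the same measure. A site following section 7.3 would ask for a rating of a therapist whom the young person has not met and whom those later allocated to the control arm will not meet in the trial. Range checks built on 5 to 20 would not fit the scale.

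**Working it through.** **Timing.** Table 1: once, halfway through BA. Section 7.3: at baseline. Randomisation follows completion of the baseline measures, so no BA therapist exists for the participant at that point. The two places conflict, and the baseline listing cannot serve the stated purpose of the measure. It therefore does not supply an alliance score for early leavers.

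**Whether another source supplies that score.**
- Young person's end-of-treatment questionnaire (section 3.3.1): given at stopping, but covers engagement, the website, preferred mode of delivery and barriers, not alliance.
- BA Completion Form (section 3.3.1): number of sessions and reasons for departing from eight.
- Session log (section 3.3.1): mode, who was present and problems, completed by the therapist after each session.
- Early-exit interviews (section 10.2): 15 young people who never start BA, so have no alliance to rate.
- Interviews sampled by engagement level (sections 10.2 and 10.3): qualitative, and limited to those who agreed to be contacted.

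None gives a WAI-S score for someone who attended one to three sessions.

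**How many could be affected.** The protocol gives no figure, so only a bound is possible. Inputs: feasibility attendance with mean 6.6 and median 8 of 8 sessions, n = 36 (section 1); BA arm of 223 (section 9.1). Assumptions: feasibility attendance carries over, and halfway means session 4.

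Mean sessions missed = 8 − 6.6 = 1.4. If every missed session came from people who stopped at exactly s sessions, their share would be 1.4 / (8 − s):
- s = 1: 1.4 / 7 = 20.0%, or 0.200 × 223 ≈ 45
- s = 2: 1.4 / 6 = 23.3%, or 0.233 × 223 ≈ 52
- s = 3: 1.4 / 5 = 28.0%, or 0.280 × 223 ≈ 62

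The case s = 0 (17.5%, about 39) is left out because those young people have no therapist to rate. The ceiling is 28%. The lower bound is 0, since the same mean could arise entirely from people who stopped after session 4.

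**Possible size of the bias.** Observed mean minus full mean = (share missing) × (difference between those who stay and those who leave). The documents give no difference, so take 0.25 to 1.0 SD as an assumed range:
- 5% missing: 0.05 × 0.25 = 0.01 SD to 0.05 × 1.0 = 0.05 SD
- 28% missing: 0.28 × 0.25 = 0.07 SD to 0.28 × 1.0 = 0.28 SD

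**Score range.** With k items scored 1 to 5, a domain runs from k to 5k. Four items give 4 to 20; five give 5 to 25. A minimum of 5 needs k = 5 and a maximum of 20 needs k = 4, so no k gives 5 to 20.

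**Therapist form.** The section 3.3.1 wording can mean all eight sessions, all sessions actually held with one young person, or a therapist's whole caseload. Table 2 fits the second reading as well as the first. Only the first clearly leaves out early leavers.

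**The case against.** The strongest case against is that little depends on the WAI-S. It is listed among the additional measures, the protocol does not name it as an acceptability outcome, and it plans no analysis of alliance against drop-out. A fixed mid-treatment reading is a legitimate choice, and ratings taken at stopping mix time points. The 28% is a mathematical ceiling from a sample of 36 whose median attendance was the full eight sessions. All of that stands and limits the weight of the point. It does not remove the gap: a fixed reading is sound only if the report says whom it omits.

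A reader might go further and infer that early leavers are missing from the acceptability data as a whole, so that BA will look more acceptable than it was. The documents do not support this. Young people's own views are collected when they stop, and that questionnaire feeds the acceptability measures; interviews also sample low engagement deliberately.

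A reader might also infer that therapist-reported barriers come only from finished courses. That is contradicted by the session log after every session, by the reasons recorded on the completion form, and by the invitation of all therapists to interview, including those who left the study early. The gap in the therapist questionnaire depends on one reading of an ambiguous sentence, so unclear wording is as far as that criticism goes.

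**Conclusion.** The point holds for the alliance measure. As scheduled, WAI-S scores describe only young people who reached the halfway point of BA. Those who leave after halfway do have a score. The omitted share is somewhere from 0 to 28% of the BA arm, on the assumptions that feasibility attendance carries over and that halfway is session 4. That the results would be too favourable is plausible but assumed; at the ceiling, an assumed deficit of 0.25 to 1.0 SD would raise the observed mean by 0.07 to 0.28 SD.

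Two errors need no assumption: the baseline listing in section 7.3 contradicts Table 1, and the 5 to 20 domain range is impossible. The MFQ-C primary analysis and young people's own acceptability data are unaffected. This is a cheap improvement to a process measure, not a threat to the trial's main conclusion.

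**What to change.** 1. Reconcile section 7.3 with Table 1 by removing the WAI-S from the baseline battery.
2. In Table 1 and section 3.3.1, collect the WAI-S halfway through BA or, if the young person stops earlier after at least one session, at stopping. Send it with the end-of-treatment questionnaire, through the unblinded team member who already distributes that form, so research assistants stay blind.
3. Define halfway. Report mid-treatment and at-stopping scores separately (4+ and <4 sessions), each with the number missing.
4. Correct the domain range to match the number of items in the version used.
5. State in section 3.3.1 and Table 2 that the therapist form is completed for each young person after the last session held, including when BA ends early.

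The cost is a wording amendment and one short form at a contact already planned. Section 9.1 shows that data collection is under way, so the rule helps only from its adoption; for young people who stopped earlier, report how many never reached the WAI-S point, using the session counts on the completion form. The downside is that early leavers rate alliance after fewer sessions, so the two sets of scores should not be pooled without comment.
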